Even in extreme plaque accumulation conditions, thorough oral hygiene and mechanical plaque removal is reported to reduce gingivitis and restore health. Control of supra gingival plaque is an essential element in effective oral hygiene programs. Oral hygiene devices are under continuous review for efficacy and safety, as new devices or improvements of features on existing devices are developed.

2. Study Objective

The primary objective of this exploratory study is to evaluate the efficacy of an Oral Irrigator in the reduction of gingivitis compared to a negative control over a 3 week period by using the Modified Gingival Index and the Gingival Bleeding Index.

The secondary objective is to evaluate the efficacy of an Oral Irrigator in the reduction of plaque compared to a negative control using the extended Turesky Modified Quigley-Hein Index (TQHPI) after 3 weeks of use.

3. Overall Study Design and Plan

This is a single-center, examiner-blind, three (3) week, two (2) treatment, parallel group, randomized study design. Thirty (30) subjects who have shown evidence of gingivitis and plaque will be enrolled in this study. Subjects will be evaluated for gingivitis using the Modified Gingival Index (MGI) and the Gingival Bleeding Index (GBI) and evaluated for plaque using the Turesky Modified Quigley-Hein Plaque Index (TQHPI) at two (2) time points: Baseline and after three (3) weeks of product use. Prior to each visit (Baseline and Week 3) subjects will be instructed to abstain from brushing and performing any oral hygiene 12 hours prior and to abstain from eating, drinking (small sips of water will be allowed up to 45 minutes prior to the visit), chewing gum and tobacco use for four (4) hours prior to the visits.

Qualified subjects will be stratified and randomly assigned to one of the two treatment groups, toothbrushing on conjunction with an Oral Irrigator or toothbrushing without an Oral Irrigator, (N=15/treatment) based on Baseline gingivitis (MGI) score, Baseline whole mouth mean TQHPI score, Baseline number of bleeding sites, and tobacco use. Subjects will be given product use instructions and asked to perform a supervised usage of their assigned products. Subjects will be instructed to brush twice a day for approximately three (3) weeks with their assigned products and return for plaque and gingivitis measures at approximately three (3) weeks after the Baseline visit. Specific procedures are detailed below (Table 1).

Table 1. Study Schedule by Procedure Type and Visit

PROCEDURE	BASELINE	WEEK 3
Informed Consent	X	
Medical History Review	X	
Demographics	X	
Inclusion/Exclusion Criteria	X	
Continuance Criteria		X
Oral Examination	X	X
Gingivitis Evaluation (MGI)	X	X
Gingival Bleeding Evaluation (GBI)	X	X
Plaque Exam (TQHPI)	X	X
Treatment Randomization/Balance and Assignment	X	
Product Distribution	X	
Oral Hygiene Instructions	X	
Product usage	X	
General Comments	X	
Product Return		X
AEs	X	X
Subject Accountability		X

Baseline

Subjects will be asked to read and sign an informed consent, of which they will receive a signed copy. Medical history information will be obtained, reviewed, and retained as site source documentation. Demographic information and study inclusion/exclusion criteria will be obtained and documented on the appropriate electronic case report form (eCRF). Subjects will be eligible to enroll in the study after meeting study entrance criteria.

Subjects will then receive an Oral Examination by an experienced examiner. Then the subjects will receive an MGI and GBI examination, in that order. Following that, subjects swish their mouth with disclosing solution and an experienced examiner will conduct a pre-brushing plaque exam: Turesky Modified Quigley-Hein Index (TQHPI). Subjects will qualify for participation if they have a baseline whole mouth mean MGI score between 1.75 and 2.5, a Baseline whole mouth mean TQHPI score (≥ 2.00), and between 20 and 80 bleeding sites. All the data will be recorded on the appropriate eCRF.

Qualified subjects will be randomized to a treatment group and receive their test products. Subjects will proceed to an area separated from the examination area to receive supervised oral hygiene instructions and product usage instructions. Subjects will brush according to the provided usage instructions with their assigned oral hygiene products (toothbrush and toothpaste with/without Oral Irrigator). The group with the Oral Irrigator will also use the device before brushing with the provided toothbrush and toothpaste. This on-site practice brushing will be considered one of the subject's two daily brushings. Subjects will be instructed to use their assigned products twice per day,

following the provided usage instructions for approximately 3 weeks. The Oral Irrigator will only be used once a day at the evening brushings.

Prior to leaving the clinic, subjects will be scheduled for their next visit (Week 3, \pm 2 days) and reminded to refrain from using their oral hygiene products for 12 hours and refrain from eating, chewing gum, drinking (small sips of water will be allowed up to 45 minutes), and tobacco use for 4 hours prior to their next visit.

Any Adverse Events or general comments will be recorded on the appropriate eCRF. All serious AEs will be reported. As for non-serious AEs, only voluntarily reported whole body adverse events that are potentially product related will be reported as will all oral related Adverse Events.

Week 3 (\pm 2 day):

Subjects will return to the site and bring their test products. Continuance criteria will be assessed and recorded on the appropriate eCRF. Subjects will then receive Oral Examination, MGI, and GBI assessments (in that order) by the experienced examiner. Following that, subjects will swish their mouth with disclosing solution and the same experienced examiner will conduct a pre-brushing plaque exam: Turesky Modified Quigley-Hein Index (TQHPI).

Any Adverse Events or general comments will be recorded on the appropriate eCRF. All serious AEs will be reported. As for non-serious AEs, only voluntarily reported whole body adverse events that are potentially product related will be reported as will all oral related Adverse Events.

Subject accountability will be recorded on the appropriate eCRF and subjects will be dismissed from the study. Subjects must return all test products in order to be exited from the study.

4. Inclusion Criteria

In order to be included in the study, each subject must:

- give written informed consent and receive a copy of the signed Informed Consent form;
- be at least 18 years of age;
- typically use a manual toothbrush;
- be in good general health as determined by the investigator/designee based on a review/update of their medical history;
- possess a minimum of 16 scorable teeth (excluding third molars) with facial and lingual scorable surfaces;
- have a Baseline MGI score between 1.75 and 2.5;
- have a Baseline TQHPI score of at least 2.00;
- have a Baseline between 20 and 80 Bleeding sites;
- abstained from all oral hygiene procedures for approximately 12 hours prior to this visit and agree to do the same prior to the subsequent visit;
- abstained from eating, drinking*, chewing gum and using tobacco for at least 4 hours prior to this visit and agree to do the same prior to the subsequent visit. *(Exception: Allowed small sips of water up until 45 minutes prior to their appointment time.)
- agree not to participate in any other oral care study for the duration of this study;
- agree to delay any elective dentistry, including dental prophylaxis, and to report any non-study dentistry received during the course of this study;
- agree to refrain from using any non-study toothbrushes, dentifrices, mouth rinses, tooth whitening products or floss for the study duration;
- agree to return for their scheduled visits and to follow all study procedures.

5. Exclusion Criteria

Subjects are excluded from study participation where there is evidence of:

- hypersensitivity to dyes;
- severe periodontal disease, as characterized by purulent exudate, generalized mobility, and/or severe recession;
- any carious lesions requiring restorative treatment;
- active treatment for periodontitis;
- any fixed facial orthodontic appliances or retainers;
- use of any antibiotic medication or a prescription mouth rinse any time within the 2 weeks prior to study initiation;
- any disease or conditions that could be expected to interfere with examination; procedures or the subject safely completing the study.

6. Continuance Criteria

Subjects may be excluded from the study or the analysis due to:

- receiving any non-study dentistry, including dental prophylaxis, since their last study visit;
- performing any oral hygiene procedures any time within approximately 12 hours prior to each visit;
- having eaten, drank*, chewed gum or used tobacco any time within the 4 hours prior to each visit. *(Exception: Allowed small sips of water up until 45 minutes prior to their appointment time);
- using any antibiotics or a prescription mouth rinse any time since their last study visit;
- using any oral care products other than assigned study products including tooth whitening products since their last study visit;
- participation in any other oral care study since their last study visit.

7. Identity of Investigational Product(s)

Type of Regimen	Oral Irrigator	Toothbrush	Dentifrice
Test	Oral-B Water Flosser advanced cordless irrigator "Aquacare 6" (MDH20.3) with Nozzle "AquaFloss" ED17	Indicator Soft 35 (OM010I-AP)	Crest Cavity Protection toothpaste
Control		Indicator Soft 35 (OM010I-AP)	Crest Cavity Protection toothpaste

8. Product Usage

Test Regimen

Subjects will use the Oral Irrigator according to the verbal and written use instruction in the evenings before they brush their teeth. Afterwards they will brush their teeth for one minute with the products provided. Subjects will rinse their mouth with water after brushing to remove excess paste.

The Oral Irrigator will be used through all teeth are reached with the device. If necessary, water can be refilled in the water reservoir. The Oral Irrigator has to be used in "continuous" stream type with focused stream (switch in upper position) and in intense mode.

Subjects will be instructed (both verbal and written) to brush their teeth with their assigned toothbrush and toothpaste for one minute twice a day for the duration of the study (approximately 3 weeks). Before the evening brushings subjects will use the Oral Irrigator as described above. Only at the Baseline Visit the Oral Irrigator will be used in the morning for device training. Brushing and use of the Oral Irrigator at the clinical site will be supervised by a site staff person.

Control Regimen

Subjects will brush their teeth for one minute with the products provided. Subjects will rinse their mouth with water after brushing to remove excess paste.

Subjects will be instructed (both verbal and written) to brush their teeth with their assigned toothbrush and toothpaste for one minute twice a day for the duration of the study (approximately 3 weeks). Brushing at the clinical site will be supervised by a site staff person.

9. Blinding, Labeling, and Shipping Plan

Test products will be supplied in subject kit boxes which are labeled with a unique kit box number. The kit boxes will be unique for each treatment leg as follows:

- **Test Group:** Oral-B® Indicator, soft 35 (OM010I-AP) manual toothbrush, overtubed Crest Cavity Protection dentifrice (0.243% NaF), Oral-B Water Flosser advanced cordless irrigator "Aquacare 6" (MDH20.3) handle with nozzle "AquaFloss" ED17, 1 charger (MDH20 charger), and a timer. The water flosser handle, nozzle, and charger will be packed in a baggie.
- **Control Group:** Oral-B® Indicator soft 35 (OM010I-AP) manual toothbrush, overtubed Crest Cavity Protection dentifrice (0.243% NaF), and a timer.

Kit boxes will be labeled with a unique kit number representing the test product and supplemental product. Kit box labels will also contain the study number, emergency phone number, distributor name/address, appropriate caution statements, and other information as required by internal regulations and clinical SOPs. The shipping containers will be labeled with the "ship to" clinical site address and a "content statement" listing study number and kit box numbers contained within. Supplemental product will be provided if additional product is needed. Supplemental product may be dispensed only after consulting with the sponsor for correct treatment group identification; the subject identification number and original kit box number must be provided to the sponsor.

The site will be provided with a code breaker report in a sealed envelope. If the study blind needs to be broken, a subject's investigational product may be ascertained by opening the sealed code breaker report (appropriate procedure for breaking the blind). The sealed code breaker report will be opened if a clinically serious AE occurs or management of the subject requires knowledge of the identity of the investigational product. The Investigator should immediately inform the Sponsor that the code will be broken and record the date, time, and reason for breaking the code in writing.

10. Method of Assigning Subjects to Treatment Groups

Subjects who meet enrollment criteria will be stratified based on Baseline MGI (≤ 2.4 vs > 2.4), Baseline number of bleeding sites (≤ 45 vs > 45), Baseline whole mouth mean TQHPI (≤ 3.0 vs. > 3.0) and smoking status (yes/no). Subjects will then be randomized to one of the two (2) treatment groups using a balance and assignment procedure on site. This assignment process and the distribution of test products will be conducted in a protected area that will ensure blinding

of the examiner to the identity of the test products. Product will be distributed according to a randomization schedule provided by the Sponsor. Product distribution and product return will be recorded on the Clinical Materials Inventory provided by the Sponsor. Subjects from the same household will be assigned to the same treatment group.

11. Determination of Sample Size

Thirty (30) subjects, 15 per treatment group, will be enrolled in this study. The sample size was based on logistical considerations.

12. Safety Variables

Safety Observations and/or Measurements

Safety will be assessed by the absence of irreversible side effects. Adverse event (AE) data will not be solicited by the clinical investigation staff. However, all AEs will be recorded in eCRF.

Oral Examination

Assessment of the oral soft tissue will be conducted via a visual examination of the oral cavity and perioral area utilizing a standard dental light, dental mirror, and gauze. The examined structures will include the gingiva (free and attached), hard and soft palate, oropharynx/uvula, buccal mucosa, tongue, floor of the mouth, labial mucosa, mucobuccal/mucolabial folds, lips, and perioral area. Assessment of the oral hard tissues will be conducted via a visual examination of the dentition and restorations utilizing a standard dental light, dental mirror, and air syringe. All abnormal findings will be recorded and categorized by their location; hard tissue findings will be categorized as "other oral". An AE will be recorded if a new abnormal finding is noted after investigational product usage or any previously noted abnormal finding increases in severity during a treatment period.

Examiner: [name], RDH, BSEd, MS

13. Efficacy Variables

The same examiner will evaluate clinical measurements for each subject at all time points. The examiner will be blinded as to the treatment assigned to each subject in each period. Clinical information will be recorded for all scorable teeth present excluding 3rd molars, teeth with crowns, or large restorations, i.e., covering 50% or more of the tooth surface, bridges, orthodontic appliances, or implants.

The order of clinical measurements will be as follows:

- A. Modified Gingival Index**
- B. Gingival Bleeding Index**
- C. Turesky Modified Quigley-Hein Plaque Index (extended)**

A. Modified Gingival Index (MGI):

Gingivitis will be scored on the buccal and lingual marginal gingival and interdental papilla of all scorable teeth (six scores per tooth):

0 = normal (absence of inflammation)

1 = mild inflammation (slight change of color, little change in texture) of any portion of the gingival unit

2 = mild inflammation of the entire gingival unit

3 = moderate inflammation (moderate glazing, redness, edema and/or hypertrophy) of the gingival unit
 4 = severe inflammation (marked redness and edema/hypertrophy, spontaneous bleeding or ulceration) of the gingival unit

MGI whole mouth score is computed by summing the scores and dividing by the number of scorable sites examined.

Examiner: [name], RDH, BSEd, MS

B. Gingival Bleeding Index (GBI): as defined by Saxton and van der Ouderaa.

The gingiva should be lightly air-dried and a periodontal probe with a 0.5 mm diameter tip inserted into the gingival crevice to a depth of 2mm or until slight resistance is felt. The probe is then run gently around the tooth at an angle of approximately 60° and in contact with the sulcular epithelium. Minimum axial force is used to avoid undue penetration into the tissue and the probe is moved around the crevice, gently stretching the epithelium. Each of the 3 gingival areas, i.e., buccal, mesial/dystal and lingual, of the teeth will be probed in this manner waiting approximately 30 seconds before recording the number of gingival units which bleed, according to the following scale:

0 = absence of bleeding after 30 seconds

1 = bleeding observed after 30 seconds

2 = immediate bleeding observed

GBI whole mouth score is computed by summing the scores and dividing by the number of scorable sites examined.

Examiner: [name], RDH, BSEd, MS

C. Turesky Modified Quigley-Hein Plaque Index (extended)

The plaque deposits on the teeth will be scored on six sites (distobuccal, midbuccal, mesiobuccal, distolingual, midlingual and mesiolingual) of all 28 teeth (excluding buccal surfaces of the upper 1st and 2nd molars, 3rd molars, crowns and surfaces with cervical restorations) according to the Quigley-Hein Index as modified by Turesky et al. which emphasizes plaque in contact with the gingival. Buccal, lingual, and whole mouth average plaque scores will be calculated for each subject and tooth surfaces by totaling the scores and dividing by the number of gradable sites examined (the examiner will score all 168 sites however the whole mouth mean will later be computed from only 162 sites - the 6 sites used in the plaque sampling will be excluded from plaque calculation). Scoring criteria are shown below.

Scoring criteria are shown in Table 2.

Table 2. Turesky Modified Quigley-Hein Index

Score	Description
0	No Plaque
1	Separate flecks of plaque at the cervical margin.
2	A thin, continuous band of plaque (up to 1 mm) at the cervical margin.
3	A band of plaque wider than 1 mm, but covering less than one third of the side of the crown of the tooth.

4	Plaque covering at least one third, but less than two thirds of the side of the crown of the tooth.
5	Plaque covering two thirds or more of the side of the crown of the tooth.
8	Ungradable site
9	Missing tooth

Examiner: [name], RDH, BSEd, MS

14. Hypothesis

The following hypotheses will be investigated for each efficacy endpoint at Week 3:

Gingivitis Hypothesis:

Null Hypothesis: There is no difference between treatment groups with respect to the mean GI change from baseline (MGI, GBI, or number of bleeding sites) at 3 weeks when an adjustment is made for the respective baseline GI score.

Alternative Hypothesis: There is a difference between the treatment groups with respect to mean GI change from baseline (MGI, GBI, or number of bleeding sites) at 3 weeks when an adjustment is made for the respective baseline GI score.

Plaque Hypothesis:

Null Hypothesis: There is no difference between treatment groups with respect to the mean TQHPI change from baseline at 3 weeks when an adjustment is made for baseline TQHPI score.

Alternative Hypothesis: There is a difference between the treatment groups with respect to mean TQHPI change from baseline at 3 weeks when an adjustment is made for baseline TQHPI score.

15. Statistical and Analytical Plans

Statistical analyses for gingivitis efficacy will be based on whole-mouth average MGI, GBI, and number of bleeding sites change from baseline scores (Baseline minus Week 3). An ANCOVA will be performed to determine treatment differences on the whole mouth average gingivitis reduction with the respective baseline gingivitis score as the covariate. Baseline by treatment interaction will be investigated and included in the final ANCOVA model if significant at the 10% level. Separate analyses will be performed for each gingivitis endpoint with MGI being primary.

Statistical analyses for plaque efficacy will be based on average whole mouth TQHPI change from baseline score (Baseline minus Week 3). The 3-week plaque reduction will be analyzed for treatment differences using an ANCOVA with baseline whole mouth TQHPI score as the covariate. Baseline by treatment interaction will be investigated and included in the final ANCOVA model if significant at the 10% level.

The within-treatment differences from baseline gingivitis scores (MGI, GBI, number of bleeding sites) will be tested versus zero using a paired difference t-test. Similar within-treatment analyses will be carried out for TQHPI.

The lingual and buccal surfaces of the gingivitis and plaque endpoints will be analyzed separately for treatment differences as described above.

If the data does not satisfy the normality criterion, transforming the data or analogous nonparametric methods will be employed. Additional analyses may also be performed in order to more fully understand the data. All treatment comparisons will be considered two-sided with an $\alpha=0.10$ significance level.

Demographic and baseline variables will be summarized by treatment group, and adverse events reported or noted during the study will be documented and listed by treatment group.

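### Adverse events are not solicited and Week 3 is the only scheduled contact after Baseline, so mild oral complaints that resolve untreated before then are listed only if volunteered

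*Combined protocol and SAP*

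**What the plan says.** Section 12 (Safety Variables) sets the method of ascertainment: "Adverse event (AE) data will not be solicited by the clinical investigation staff". The next sentence adds: "However, all AEs will be recorded in eCRF". The sentence before it gives the safety criterion, which is that no irreversible side effects occur.

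Section 3 (Overall Study Design and Plan) gives the reporting rule, in the same words at both visits. All serious events are reported. For non-serious events, "only voluntarily reported whole body adverse events that are potentially product related will be reported as will all oral related Adverse Events".

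On contacts, Section 3 places the efficacy assessments at "two (2) time points: Baseline and after three (3) weeks of product use". Table 1 has the same two columns. AEs are marked in both, and the Oral Examination is done at both. Between the visits, subjects use their products at home, "following the provided usage instructions for approximately 3 weeks. The Oral Irrigator will only be used once a day at the evening brushings".

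On analysis, Section 15 says that "adverse events reported or noted during the study will be documented and listed by treatment group". No test between arms is planned for adverse events.

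**The concern.** The plan promises fuller capture than its method can deliver. It undertakes to record every adverse event and to report every oral one. However, subjects spend about three weeks at home, nobody is scheduled to contact them, and on their return staff do not ask. The Week 3 oral examination is visual and shows the mouth as it is on that day. Soreness or irritation that came and went leaves nothing for it to find.

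Two consequences follow for the listing by treatment group. First, it can undercount mild, self-limiting oral complaints in either arm. Second, the undercount need not be equal. One kit contains an irrigator and the other does not, so every subject knows the assignment. A subject given a device may be more or less inclined to mention a complaint than one given only a toothbrush, and the direction cannot be known in advance. The listing is laid out by arm and will be read as a comparison, even though no test is planned.

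**Working it through.** **Routes into the record.** The plan states no adverse event rate and no figure to reproduce, so the first step is to ask how a complaint that arose after Baseline could be recorded.

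| Route | Source | Captures a complaint resolved before Week 3? |
|---|---|---|
| Oral examination, blinded examiner | Sections 3, 12 and 13 | No; only findings new or worse on that day |
| Staff question about symptoms | Section 12 | Not asked |
| Continuance criteria at Week 3 | Section 6 | Only indirectly, if the complaint led to dentistry, antibiotics, a prescription rinse or a non-study oral care product |
| Interim visit, call or diary | Section 3, Table 1 | None scheduled |
| Emergency number on the kit label, or a request for supplemental product | Section 9 | Only if the subject makes contact and mentions it |
| Subject's own remark at Week 3 | Section 3 | Only if volunteered |

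For a mild complaint that resolved untreated, every open route depends on the subject raising it. Complaints that are still visible, or that led to treatment, have another way in.

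**Illustrative size.** The only input from the documents is n = 15 per arm (Section 11). The rest is assumed:

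- p, the share of test subjects with a transient oral complaint: 5% or 20%.
- v, the share of those who volunteer it: 30% or 60%, against v = 100% as a full-capture benchmark.
- Subjects are independent, and no complaint is still visible at the Week 3 examination.

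Expected recorded cases = n × p × v. Probability that none is recorded = (1 − p × v)^n.

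| p | v | Expected cases | P(no case recorded) |
|---|---|---|---|
| 20% | 100% | 15 × 0.20 = 3.0 | 0.80^15 = 3.5% |
| 20% | 60% | 15 × 0.12 = 1.8 | 0.88^15 = 14.7% |
| 20% | 30% | 15 × 0.06 = 0.9 | 0.94^15 = 39.5% |
| 5% | 100% | 15 × 0.05 = 0.75 | 0.95^15 = 46% |
| 5% | 60% | 15 × 0.03 = 0.45 | 0.97^15 = 63% |
| 5% | 30% | 15 × 0.015 = 0.225 | 0.985^15 = 80% |

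The v = 100% rows flatter the remedy, because a question at Week 3 will not recover every complaint from the first week. If asking captured 80%, the p = 20% figure would be (1 − 0.16)^15 = 0.84^15 = 7.3%. That is still below the 14.7% to 39.5% range.

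**What an empty listing would show.** With no cases in 15 subjects and full capture, the one-sided 95% upper bound on incidence is 1 − 0.05^(1/15) = 18%. If only half of complaints are volunteered, that bound applies to p × v, so the bound on p is 0.181 / 0.5 = 36%.

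**The case against.** The strongest reply is that the plan does what it set out to do. It is exploratory, both objectives concern efficacy, and the sample size is logistical. Its stated criterion is the absence of irreversible side effects, and irritation that has healed is by definition reversible. The main structured safety measure is the oral examination, which is the same in both arms, done by a blinded examiner and independent of what the subject chooses to say. Not soliciting events is openly stated. All of this stands. It is why the point has low priority and touches neither the primary MGI analysis nor the safety criterion. It does not reconcile the non-solicitation rule with the commitments to record all adverse events and report all oral ones.

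A second reply is that the size rests on assumption. This is also right. The documents support neither the incidences nor the volunteering rates. At 5% incidence, even perfect elicitation leaves the listing empty almost half the time. Subjects also enter with gingivitis and 20 to 80 bleeding sites (Section 4), so some answers to a general question would reflect background disease.

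A reader might infer more than the documents support:

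- That staff are barred from recording what they hear. Section 12 is a statement of method, and it goes on to say that all events are recorded.
- That the irrigator is a new device with a known irritation risk. Section 7 gives only a product name and model number, and no such risk is described.
- That the comparison of adverse events between arms is biased. Differential volunteering is possible, but nothing shows that it occurs or in which direction, and no formal comparison is planned.

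**Conclusion.** The point holds within narrow limits. Mild oral complaints that arise during home use and resolve untreated before Week 3 are recorded only if volunteered. The listing by arm may therefore be incomplete, and may be unequally so. This follows from Section 12 read with the visit schedule and needs no assumed rate. The size does need assumed rates: at 20% incidence the chance of an empty test-arm listing rises from 3.5% to about 15% to 40%, and at 5% from 46% to 63% to 80%, taking volunteering at 60% down to 30%. These figures show the order of the effect and are not estimates for this device.

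The documents do not support the further conclusion that the safety assessment as a whole fails. The oral examination covers what is present at Week 3, and the stated criterion concerns irreversible effects. The change is worth making because it is cheap, not because a trial conclusion depends on it.

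**What to change.** In Section 12 and Table 1, replace the non-solicitation rule with one standard, non-leading question put to every subject in both arms at Week 3. An example is: have you noticed any change in your mouth or your health since the last visit? Staff other than the examiner should ask it, after MGI, GBI and plaque have been scored, so that the answer cannot unblind the examiner. Add an eCRF flag separating elicited from volunteered events, and show it in the Section 15 listing. At the same time, reconcile the Section 12 statement that all adverse events are recorded with the narrower reporting rule for non-serious whole-body events in Section 3.

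The cost is one question per subject at an existing visit and one data field. The adverse event count will be somewhat higher and will include some background complaints. Comparability with studies that did not solicit events is reduced, which the flag mitigates. The question makes prompting the same in both arms. It reduces under-capture and differential reporting but does not remove them, because recall is imperfect and subjects still know their arm.

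### Allocation is balanced on four baseline factors but the primary MGI ANCOVA adjusts for one: the test stays valid, but may be conservative and lose some power

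*Combined protocol and SAP*

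**What the plan says.** Section 10 (Method of Assigning Subjects to Treatment Groups) opens "Subjects who meet enrollment criteria will be stratified based on Baseline MGI" and goes on to bleeding sites, TQHPI and smoking, each split in two (2.4 for MGI, 45 for bleeding sites, 3.0 for TQHPI, yes/no for smoking). Subjects are then randomised "using a balance and assignment procedure on site"; the algorithm is not described. Section 3 gives the same four factors, its list ending "Baseline number of bleeding sites, and tobacco use".

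Section 15 analyses change from baseline by ANCOVA "with the respective baseline gingivitis score as the covariate", and states: "Separate analyses will be performed for each gingivitis endpoint with MGI being primary". The plaque ANCOVA has baseline TQHPI as its only covariate. The buccal and lingual analyses use the same models. Section 14 writes the single adjustment into the gingivitis hypotheses: "when an adjustment is made for the respective baseline GI score". Only one further term can enter: "Baseline by treatment interaction will be investigated and included in the final ANCOVA model if significant at the 10% level". Section 15 also permits unspecified additional analyses, but names no covariates for them.

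Section 11 sets 30 subjects, 15 per group, on logistical grounds. Section 15 tests two-sided at 0.10.

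**The concern.** Balancing on a prognostic factor removes much of that factor's variation from the difference between arms. If the analysis model leaves the factor out, the same variation stays in the residual mean square. The standard error then describes a less precise comparison than the one the design delivered, so the test rejects too rarely under the null and loses power under the alternative.

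The primary endpoint is exposed to this. The MGI model lacks bleeding sites, TQHPI and smoking, although all three are recorded at Baseline and used to allocate. The study is exploratory, has no planned power, and already accepts a 10% error rate, so a missed signal is the error that matters most here.

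**Working it through.** **Factors against model terms**

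| Balancing factor (Sections 3, 10) | MGI model | GBI model | Bleeding-site model | TQHPI model |
|---|---|---|---|---|
| Baseline MGI | yes | no | no | no |
| Bleeding sites | no | no (own baseline GBI comes from the same probing) | yes | no |
| TQHPI | no | no | no | yes |
| Smoking | no | no | no | no |

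The plan states no power figure, so there is none to reproduce.

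**Inputs.** From the documents: 15 per arm, two-sided alpha 0.10, four two-level factors. Assumed, because the documents are silent: R², the share of variance left after baseline MGI that the three omitted factors explain (0 to 0.3); an effect of 0.8 SD; minimisation on the four factors, choosing the better-balancing arm with probability 0.9 to 1.0 (called tight); MGI cut at its 85th percentile, and bleeding and TQHPI at the median; 25% or 40% smokers; correlation 0 or 0.3 between baseline scores; omitted factors equally weighted.

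**Anchor for power.** The noncentrality is 0.8 × √(15/2) = 2.19. On 27 df with critical t 1.703, power is about 69% before any allowance for chance imbalance in baseline MGI. The simulation gives 67 to 68% at R² = 0.

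**Limiting case for type I error.** If balance on the omitted factors were exact, the null t statistic would be shrunk by about √(1 − R²). Type I error would then be roughly P(|t₂₇| > 1.703/√(1 − R²)):
- R² = 0.1: 1.703/0.949 = 1.795, giving 8.4%
- R² = 0.2: 1.703/0.894 = 1.904, giving 6.8%
- R² = 0.3: 1.703/0.837 = 2.036, giving 5.2%

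Real procedures balance only dichotomised factors, and imperfectly, so true values should lie between these and 10%.

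**Simulation, tight balancing, 30 analysed** (40,000 runs; Monte Carlo error about 0.15 points for type I error and 0.25 for power):

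| R² | Type I error %, planned / adjusted | Power %, planned / adjusted | Change, points |
|---|---|---|---|
| 0 | 9.7–10.2 / 9.8–10.2 | 67.3–67.6 / 65.0–65.2 | −2.2 to −2.5 |
| 0.1 | 9.0–9.2 / 10.0–10.2 | 68.3–68.4 / 69.3–69.5 | +0.9 to +1.2 |
| 0.2 | 8.1–8.4 / 10.0–10.2 | 68.4–68.6 / 73.6–73.8 | +5.1 to +5.2 |
| 0.3 | 7.0–7.6 / 9.9–10.2 | 68.9–69.4 / 78.6–79.0 | +9.6 to +9.8 |

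Break-even under tight balancing (120,000 runs): −0.56, −0.06 and +0.20 points at R² = 0.06, 0.07 and 0.08.

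**Sensitivity of the power change (points)**

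| Setting | R² = 0 | 0.1 | 0.2 | 0.3 |
|---|---|---|---|---|
| Weaker balancing (0.7) | −3.5 | −0.1 | +4.3 | +8.9 |
| No balancing | −5.0 | −0.6 | +3.6 | +8.6 |
| 26 analysed (0.9) | −3.4 | +0.5 | +4.5 | +9.4 |
| Effect 1.0 SD | −2.4 | +0.7 | +3.4 | +6.2 |

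Planned type I error at R² = 0.1, 0.2 and 0.3 is 9.6%, 8.9% and 8.6% with weaker balancing, and 9.8 to 10.3% throughout with none. Interpolating the no-balancing row gives break-even at 0.1 + 0.1 × 0.6/(0.6 + 3.6) = 0.114.

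**Cross-check with a different set-up.** Here the outcome depends on the stratum indicators, the baseline-score correlation is 0.4, the effect is 0.9 SD, and allocation is by minimisation at 0.9 or stratified blocks of two. Planned type I error is about 9% at R² = 0.1 and 5.9 to 6.8% at 0.3. The power change is between −1 and −2 points at R² = 0, +2 to +3 at 0.1 and +8 to +9 at 0.3. The pattern is the same.

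The main runs leave out the baseline-by-treatment interaction step. A run that included it moved each power figure by about 0.5 points and left the contrast unchanged.

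**The case against.** The strongest reply is that nothing is broken. ANCOVA on the endpoint's own baseline is a coherent analysis, stated consistently in Sections 14 and 15. The benefit of adding terms rests on an R² that the documents do not give, and below break-even the larger model is slightly worse. R² here means variance beyond baseline MGI, and eligibility already narrows MGI to 1.75–2.5 and bleeding to 20–80 sites, which may limit what the other baselines add. The conservatism also depends on an undescribed allocation procedure and vanishes if that procedure does not balance. The study is exploratory, has no power target, and allows additional analyses.

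Most of this stands, and it sets the weight of the point. Two parts do not dispose of it. The clause on additional analyses commits to no covariates, so an adjusted model fitted under it would be chosen after the data are seen. And the plan gives no reason for leaving out factors that it thought worth balancing.

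A reader might infer more: that the omission biases the treatment effect, inflates false positives or invalidates the primary test. The documents do not support that, since the error runs towards conservatism. A reader might also take the choice to balance on these factors as evidence that they are strongly prognostic, and so treat the power loss as certain. The documents contain no such evidence.

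**Conclusion.** The mismatch holds as a minor efficiency point. The primary MGI model omits three of the four balancing factors, and smoking is in no model; bleeding sites and TQHPI do appear as covariates in their own endpoint models. The planned test is valid and unbiased.

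Under tight balancing it gives up about 5 points of power at R² = 0.2 and 10 at R² = 0.3, for an assumed 0.8 SD effect, and its true type I error falls to about 8% and 7.0 to 7.6%. At R² = 0.1 the difference is about 1 point, and below about 0.07 the planned model is the better one. With no balancing there is no conservatism, and break-even rises to a little above 0.1. The direction of the effect on size is secure. Its amount rests on an assumed R², balancing strength and effect size.

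**What to change.** Before the first subject is randomised, pre-specify in Section 15 main effects for the remaining balancing factors, with baseline scores continuous and smoking as the yes/no value used at allocation:

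- MGI model: add bleeding sites, TQHPI and smoking.
- Bleeding-site and GBI models: add MGI, TQHPI and smoking. Baseline GBI presumably stands in closely for the bleeding count, since Section 13 takes both from one probing.
- TQHPI model: add MGI, bleeding sites and smoking.

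Do not fit the 2⁴ = 16 stratum cells (30/16 = 1.9 subjects each). Limit the interaction check to the endpoint's own baseline. Reword the Section 14 hypotheses to match, and report the one-covariate model as a sensitivity analysis.

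The cost is text edits and no new data. Error degrees of freedom fall from 27 to 24 (critical t 1.703 to 1.711), or from 23 to 20 (1.714 to 1.725) if 26 are analysed. If the factors explain nothing, power falls by 2 to 3 points under tight balancing, about 3.5 with weaker balancing or four exclusions, and up to 5 with no real balancing. Any conservatism in the planned test is given up: type I error returns to the nominal 10%.
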